4.2. Exclusion Criteria

Patients will be excluded from the study if any of the following exclusion criteria are met. Patients cannot be enrolled before it is determined that the patient does not meet any of the exclusion criteria (including test results).

1. History of any comorbidity that, in the opinion of the Investigator, could confound the results of the study, pose an additional risk from the IP or study procedures, could potentially contribute to the clinical instability of the subject during the study, or would make the subject unlikely to complete the study. This may include, but is not limited to a history of cardiovascular, renal, or central nervous system disease; history of serious mental illness; history or presence of clinically significant pathology including liver cirrhosis and/or portal hypertension; and history of uncontrolled CF-related diabetes.
2. An acute upper or lower respiratory infection, pulmonary exacerbation, or clinically significant episode of hemoptysis (>30 mL or in the opinion of the Investigator) within 28 days prior to Day 1.
3. Any of the following changes in medication prior to Day 1:
 - Any change in chronic respiratory medication within 28 days prior to Day 1.
 - Initiation of any new chronic therapy (eg, inhaled hypertonic saline, or inhaled antibiotic (tobramycin [TOBI], aztreonam [CAYSTON])) within 28 days prior to Day 1.
 - Use of antibiotics or oral steroids for acute symptoms within 14 days prior to Day 1.
4. Receiving treatment with ivacaftor monotherapy (KALYDECO).
5. Parts A and B only: Receiving treatment with triple combination therapy (TRIKAFTA). Patients with a prior history of treatment with TRIKAFTA are eligible to participate if treatment has been discontinued at least 28 days prior to Day 1.
6. Patients with a Class III, IV, or V CFTR gene mutation in at least 1 allele.
 - See [Appendix 2](#) for guidance on the classification of CFTR mutations. (As the phenotype and classification of some CFTR mutations remains uncertain, the eligibility of a patient with 1 of these mutations will be at the discretion of the Investigator and Sponsor, based on the patient's medical history).
7. Any of the following abnormal laboratory values at screening:
 - Hemoglobin <10 g/dL.
 - Serum albumin <2.5 g/dL.
 - Abnormal liver function defined as meeting any 3 or more of the following: ALT $>3x$ upper limit of normal (ULN); AST $>3x$ ULN; GGT $>2.5x$ ULN; alkaline phosphatase $>2.5x$ ULN; and total bilirubin $>1.5x$ ULN (except for patients with isolated Gilbert Syndrome).

8. Any clinically significant abnormal laboratory test result prior to Day 1 that would interfere with the study assessments or indicate clinical instability of the patient, as judged by the Investigator.
9. Infection with highly virulent bacteria associated with accelerated decline in pulmonary function and/or decreased survival (eg, *Burkholderia cenocepacia*, *Burkholderia dolosa*, *Mycobacterium abscessus*). For a patient with a history of positive culture, he/she can be considered free of infection based on the following guidance:
 - All cultures obtained within the past 12 months should be negative for these bacteria. The patient should have had at least 2 cultures performed within the past 12 months, at least 3 months apart, with at least 1 culture obtained within 6 months of screening for this study.
10. History of or listed for solid organ or hematological transplantation.
11. Positive viral serology test results for HIV type 1 or 2 antibodies, hepatitis B surface antigen (HBsAg), or hepatitis C virus (HCV) antibodies at screening.
12. Positive test for drugs of abuse or alcohol at the screening visit.
13. Donation of blood or blood products within 60 days prior to the initial screening visit.
14. Participation in an IP or device study within 30 days prior to the initial screening visit or at any time during this Translate Bio-Sponsored study. (The 30-day window applies to IPs with elimination half-lives of <6 days. If the elimination half-life of the IP is \geq 6 days, then the window should be extended to at least 5 half-lives from the last dose administered.)
15. Prior enrollment in this study, with the exception of subjects who discontinued treatment after one dose of study drug for a reason unrelated to safety as specified in Section [7.1.1.2](#). (A patient is considered enrolled into the study when he or she has been randomized.)
16. Any suspicion of, or history of, alcohol and/or other substance abuse or addiction within the past year.
17. Pregnant or lactating females.
18. History of drug allergy or other allergy that, in the opinion of the Investigator, contraindicates participation (eg, history of allergic reactions that could interfere with the safety assessment of the IP).
19. History of allergic reactions to any component of the IP including its excipients.

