4.5.1. Reasons for Discontinuation and Individual Stopping Rules

Individual Subjects will be discontinued by the Investigator if they meet any of the stopping rules described below:

1. A significant febrile reaction defined as \geq Grade 2 fever (>39.0 °C) associated with systemic symptomatology (eg, body aches, malaise, nausea) within 24 hours following administration of IP.
2. An absolute decrease in predicted FEV1 of at least 25% compared to the baseline value (defined as the average of the Day -1 and Day 1 pre-dose values) during the 5-week treatment period in Part B or through Day 11 (1 week post-5th dose) in Part D that cannot be explained, in the opinion of the PI, by the underlying disease of CF and that is confirmed on 2 separate occasions at least 3 days apart
3. A suspected moderate to severe allergic/hypersensitivity reaction, including but not limited to anaphylaxis, generalized rash, edema or bronchospasm possibly related to drug treatment
4. Deterioration of liver function as explained below and in Section 8.1.4.1
 - a. Elevation of ALT or AST to >5 x ULN in a subject regardless of baseline value
 - b. Elevation of ALT or AST to >3 x ULN in a subject with a normal baseline or elevation of >3 x ULN from the subject's actual baseline if not normal, with the

appearance of fatigue, nausea, vomiting, right upper quadrant pain or tenderness, fever, rash, and/or eosinophilia (>5%).

c. Elevation of ALT or AST to >3x ULN in a subject with a normal baseline or elevation of >3x ULN from the subject's actual baseline if not normal, and total bilirubin >2x ULN or INR >1.5.

If any of the above criteria is met by a Part B or Part D subject who has not completed dosing with IP, treatment must be interrupted immediately and the Medical Monitor notified of this action.

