A thorough investigation of other potential causes should be conducted in all cases. If no convincing alternative etiology (eg, pre-existing CF-related liver disease, viral hepatitis, alcohol ingestion, concomitant medication [such as antibiotic treatment]) for the elevated transaminases and symptoms is identified, regardless of whether ALT or AST levels have improved, treatment of the subject must be discontinued, in consultation with the Medical Monitor. If a convincing alternative etiology for the elevated transaminases is identified and the subject's symptoms and laboratory findings have improved, the Investigator may consider resuming IP treatment with close monitoring, in consultation with the Medical Monitor.

The reason for withdrawal must be determined by the Investigator and recorded in the subject's medical record and on the CRF. If a subject is withdrawn for more than 1 reason, each reason should be documented in the source document and the most clinically relevant reason should be entered on the CRF.

Reasons for discontinuation include but are not limited to:

- AE
- Pregnancy
- Protocol deviation
- Withdrawal by subject
- Lost to follow-up
- Physician decision
- Study terminated by Sponsor
- Other (if "Other" is selected, the Investigator must specify on the CRF)

For all discontinued subjects who received the IP, every attempt must be made to follow each subject for the duration of the study.

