4.5.6. Study Stopping Criteria

IP administration will be halted for all subjects if any of the following stopping criteria are met:

- a. A subject experiences a Grade 4, life-threatening treatment-emergent AE or death that is considered probably or definitely related to IP by the Investigator
- b. Two or more subjects in a dose group experience 1 or more moderate or severe pulmonary exacerbations during the 5-week treatment period in Part B or through Day 11 (1 week post-5th dose) in Part D
- c. Two or more subjects in a dose group experience an absolute decrease in predicted FEV1 of at least 25 % compared to the baseline value (defined as the average of the Day -1 and Day 1 pre-dose values) during the 5-week treatment period in Part B or through Day 11 (1 week post-5th dose) in Part D that cannot be explained, in the opinion of the Investigator, by the underlying disease of CF and that is confirmed on 2 separate occasions at least 3 days apart
- d. Two or more subjects in the study experience a suspected serious allergic/hypersensitivity reaction, including but not limited to anaphylaxis, generalized rash or bronchospasm likely to be related to drug treatment
- e. Two or more subjects in a dose group experience a deterioration in liver function, as detailed below:
 - i. Elevation of ALT or AST to >5 x ULN in a subject regardless of baseline value
 - ii. Elevation of ALT or AST to >3 x ULN in a subject with a normal baseline or elevation of >3 x ULN from the subject's actual baseline if not normal, with the

appearance of fatigue, nausea, vomiting, right upper quadrant pain or tenderness, fever, rash, and/or eosinophilia (>5%).

- iii. Elevation of ALT or AST to >3x ULN in a subject with a normal baseline or elevation of >3x ULN from the subject's actual baseline if not normal, and total bilirubin >2x ULN or INR >1.5.

To determine whether these stopping rules have been met, all available data relating to the safety of the IP will be reviewed by the PSRC. The treatment assignment of one or more subjects may be unblinded at the request of the PSRC, as described in Section 3.4.1.2. Following this review, the PSRC will decide if the study will:

- Resume unchanged or
- Resume with modifications to the protocol or
- Be terminated.

The Sponsor is responsible for notifying the relevant regulatory authorities and the Investigator is responsible for promptly notifying the relevant IRB of the decision.

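### Exclusion 7 does not by its numbers bar an ALT or AST already above 5x ULN, a value that meets stopping rule 4a and the per-subject limb of study-halt criterion (e)(i) with no change on treatment

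*Protocol*

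**What the plan says.** **Entry.** Protocol 4.2, criterion 7 (same in the synopsis) lists five screening flags: ALT >3x, AST >3x, GGT >2.5x, alkaline phosphatase >2.5x and total bilirubin >1.5x ULN. It excludes on "Abnormal liver function defined as meeting any 3 or more of the following". No single test has a ceiling. Criterion 8 adds an exclusion left to the Investigator's discretion: "Any clinically significant abnormal laboratory test result prior to Day 1 that would interfere with the study assessments or indicate clinical instability of the patient". Criterion 1 covers comorbidity in the Investigator's opinion and names cirrhosis and portal hypertension as examples.

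**Individual stopping.** Protocol 4.5.1, rule 4, is introduced as "Deterioration of liver function as explained below and in Section 8.1.4.1". Its limb (a) reads "Elevation of ALT or AST to >5 x ULN in a subject regardless of baseline value". Limbs (b) and (c) use >3x ULN, adjust for an abnormal baseline, and also require symptoms or signs (b), or raised bilirubin or INR (c). If any limb is met by a Part B or Part D subject who has not finished dosing, "treatment must be interrupted immediately and the Medical Monitor notified of this action". On restarting treatment: "If a convincing alternative etiology for the elevated transaminases is identified and the subject's symptoms and laboratory findings have improved, the Investigator may consider resuming". Section 8.1.4.1 repeats all of this.

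**Study halt.** Protocol 4.5.6(e), repeated in SAP 2.7, halts dosing for all subjects if "Two or more subjects in a dose group experience a deterioration in liver function, as detailed below", and its limb (i) is the same >5x ULN test that disregards baseline. The PSRC reviews the data to determine whether the rule is met. It may then let the study resume unchanged, resume with modifications, or be terminated.

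**The concern.** A stopping rule should respond to something that happens after dosing. Here the entry rule counts abnormal tests without limiting any of them, while one stopping limb applies an absolute ceiling to ALT and AST whatever the starting value. A subject can therefore pass criterion 7 and already be over the stopping ceiling. Both stopping rules are framed as a deterioration, and their companion limbs are adjusted for an abnormal baseline, so the plan foresees abnormal baselines but leaves them out of account in this one limb.

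At stake is the meaning of a liver stop in a trial whose primary endpoint is safety. Each Part B dose group has 3 active subjects and 1 on placebo, so interrupting one active subject with a stable value affects a third of the active data at that dose. Two such subjects in a group bring the whole study up for review without any change on treatment.

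**Working it through.** The plan states no figure on this point, so there is nothing to reproduce. The check is logical.

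**Step 1. One worked case.** ALT 6x ULN, AST 6x ULN, other three tests below their cut-offs.

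| Test applied | Result |
|---|---|
| Criterion 7: at least 3 of 5 flags | 2 flags, not excluded |
| Rule 4a: ALT or AST >5x ULN, any baseline | met |
| 4.5.6(e)(i), per-subject limb | met |

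**Step 2. All screening patterns.** Put ALT and AST each in one of three bands (≤3x, >3x to 5x, >5x ULN) and the other three tests as flag yes or no: 3 × 3 × 2 × 2 × 2 = 72 patterns. Criterion 7 is passed with at most 2 flags.

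| ALT/AST flags | Band combinations | Allowed patterns of the other three | Pass criterion 7 | Of which ALT and/or AST >5x |
|---|---|---|---|---|
| 0 | 1 | 0 to 2 flags: 1 + 3 + 3 = 7 | 7 | 0 |
| 1 | 2 × 2 = 4 | 0 or 1 flag: 1 + 3 = 4 | 16 | 2 × 4 = 8 |
| 2 | 2 × 2 = 4 | 0 flags: 1 | 4 | 3 × 1 = 3 |
| Total | | | **27** | **11** |

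Each of the 11 meets rule 4a and the per-subject limb of (e)(i) at entry. These are counts of logical patterns, not frequencies. The band must be >5x, because values between 3x and 5x do not meet this limb.

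**Step 3. Do later checks catch a stable value?** In Parts A and B, Day -1 and Day 1 results exclude only on a clinically significant or relevant change (Protocol 7.1.1 and 7.2.2). In Part D, chemistry is not among the Day 1 eligibility tests (7.3.2). A stable value passes these checks unless the Investigator invokes criterion 1 or 8.

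**Step 4. When would the rule act?** The first scheduled on-treatment chemistry is Day 15 pre-dose in Part B (Tables 4 and 7) and Day 3 pre-dose in Part D (Table 8). The interruption wording covers subjects still dosing in those parts. Part A is a single dose.

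**Step 5. How many subjects are needed?** One for the individual rule. Two in the same dose group for the halt limb: 2 of 4 in a Part A or B group, 2 of 8 in Part D.

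**Step 6. Illustration only.** Let p be the share of enrolled subjects with ALT or AST already >5x ULN. The documents do not give p, so the values below are assumptions, with subjects taken as independent. P(at least 2 of n) = 1 − (1−p)^n − n·p·(1−p)^(n−1).

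| Assumed p | n = 4 | n = 8 |
|---|---|---|
| 1% | 0.06% | 0.27% |
| 5% | 1.4% | 5.7% |
| 10% | 5.2% | 18.7% |
| 20% | 18.1% | 49.7% |

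The finding does not depend on this table.

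**The case against.** The best defence is that criterion 7 does not stand alone. A patient must pass every exclusion, and a transaminase already over a written stopping ceiling is an obvious candidate for criterion 8 as a result that would interfere with study assessments. Criterion 1 is open-ended too. This stands in part: it would be wrong to infer that the protocol openly accepts such patients. What remains is a judgement with no number behind it, which two sites could apply differently to the same value.

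Four other strong readings also fail on the documents.

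- *The halt is automatic.* It is not. Two such subjects meet the written limb, but the PSRC determines whether the rule is met and may let the study resume unchanged. The deterioration wording gives it grounds to discount a stable value, although the limb itself disclaims baseline.
- *A stable abnormality would be counted as drug-related.* Neither rule assigns causality. Relatedness is a separate Investigator judgement (Protocol 8.1.2).
- *The plan expects to enrol subjects with liver disease, because it mentions "pre-existing CF-related liver disease".* That phrase sits in a list of example alternative causes that also names viral hepatitis and alcohol, which exclusions 11, 12 and 16 screen against. The list does not show expected enrolment.
- *An interrupted subject is lost for good.* There is a route back when another cause is found, and the Sponsor may replace subjects (4.5.2). The route is incomplete, however: it also requires laboratory findings to have improved, which a stable value does not show.

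Finally, an absolute ceiling may be a deliberate, cautious choice, and its error here is an unnecessary interruption or review rather than missed harm. That limits the consequence but does not make the entry and stopping passages consistent.

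**Conclusion.** The inconsistency is real and follows from the text alone. By its numeric terms, criterion 7 leaves eligible 11 of the 27 passing patterns in which ALT and/or AST is already above 5x ULN, and each meets rule 4a and the per-subject limb of (e)(i) unchanged. One such subject still dosing in Part B or D must be interrupted under the written rule and does not clearly qualify to resume. Two in one dose group meet the written limb for a study-wide halt, subject to PSRC review.

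This rests on the entry value staying above 5x ULN and on the Investigator not using criterion 1 or 8. Its frequency cannot be derived from the documents. It should be corrected, but it does not show that the safety oversight fails.

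**What to change.** Reconcile criterion 7 (synopsis and Protocol 4.2) with rule 4a in 4.5.1, criterion (e)(i) in 4.5.6, section 8.1.4.1 and SAP 2.7, so that a value permitting randomisation does not by itself, unchanged, satisfy a stopping criterion. The sponsor decides which passage changes and how. No threshold or clinical rule is proposed here.

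The cost is about one sentence, mirrored wherever the changed rule is repeated. No new test is needed, because serum chemistry including ALT and AST is already scheduled at screening in all three parts. If the sponsor chooses to change the entry criterion, some candidates with marked isolated transaminase elevation might no longer qualify; their number cannot be estimated from the documents.

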4.3. Restrictions

The following restrictions apply to the in-house stay in the study center (Day -1 to Day 2) for subjects participating in Part A of the study.

1. Subjects should refrain from strenuous physical exercise 48 hours prior to admission to the study center and during the in-house stay at the study center.
2. Subjects should refrain from alcohol 48 hours prior to admission to the study center and during the in-house stay at the study center.
3. Subjects will be required to eat the provided meals while housed in the study center.

4.4. Reproductive Potential

4.4.1. Female Contraception

Sexually active females of childbearing potential should be using an acceptable form of contraception. These subjects must be advised to use an acceptable method of contraception, as defined below, from the time the informed consent is signed until the final study visit on Day 337 (± 3 days) in Part A, Day 365 (± 3 days) in Part B, or Day 341 (± 3 days) in Part D of the study. If hormonal contraceptives are used, they should be administered according to the package insert.

Females of childbearing potential who are not currently sexually active must agree to use an acceptable method of contraception, as defined below, if they become sexually active during the study.

Acceptable methods of contraception are:

- Intrauterine devices plus condoms.
- Double-barrier methods (eg, condoms and diaphragms with spermicidal gel or foam).
- Hormonal contraceptives (oral, depot, patch, injectable, or vaginal ring), stabilized for at least 30 days prior to the administration of the IP, plus condoms. Note: if a subject becomes sexually active during the study, they should use one of the other acceptable methods noted above in addition to the hormonal contraceptive until it has been stabilized for 30 days.
- Females of childbearing potential currently taking the lumacaftor/ivacaftor combination drug (ORKAMBI) and using oral hormonal contraceptives will be required to take an additional or alternative method of contraception to prevent pregnancy in this study.
- Vasectomized partner (at least 6 months post-procedure).
- Exclusively same-sex (female) partner.

Female subjects of non-childbearing potential are defined as either:

- Post-menopausal (12 consecutive months of spontaneous amenorrhea and ≥ 51 years of age)

or
- Surgically sterile (having undergone one of the following procedures: hysterectomy, bilateral tubal ligation, bilateral oophorectomy, or bilateral salpingectomy) and at least 6 weeks post-sterilization.

Serum or urine β -hCG pregnancy tests will be performed on all female subjects, regardless of childbearing potential, as described in Section [7.5.2.8](#).

4.4.2. Male Contraception

All sexually active male subjects who are able to have children must agree to consistently use a barrier method from the time the informed consent is signed until the final study visit on Day 337 (± 3 days) in Part A, Day 365 (± 3 days) in Part B, or Day 341 (± 3 days) in Part D of the study. Female partners of these subjects must also use at least one of the acceptable methods of contraception listed in Section [4.4.1](#) during the same time period.

Male subjects who are able to have children must agree not to donate sperm for the purposes of making a woman pregnant from the time the informed consent is signed up to the final study visit.

For this study, male subjects will be considered as unable to have children if they are 1) infertile due to congenital bilateral absence of the vas deferens documented in the subject's medical record based on ultrasonography and/or semen analysis, 2) sterilized (vasectomy), 3) not sexually active, or 4) exclusively same sex (male) partner.

4.5. Discontinuation of Subjects and Individual Stopping Rules

A subject may withdraw from the study at any time for any reason without prejudice to their future medical care by the physician or at the institution. The Investigator or Sponsor may withdraw the subject at any time (eg, in the interest of subject safety). The Investigator is encouraged to discuss withdrawal of a subject with the Medical Monitor when possible.

If a subject is discontinued from the study, regardless of the reason, the early withdrawal evaluations listed below are to be performed as completely as possible. Comments (spontaneous or elicited) or complaints made by the subject must be recorded in the source documents. The reason for termination must be recorded in the CRF and source documents (Section [4.5.1](#)).

If enrolled subjects discontinue from the study, these subjects may be replaced at the Sponsor's discretion, as described in Section [4.5.2](#).

Early withdrawal evaluations:

- Physical examination
- Vital signs (blood pressure, pulse, body temperature, respiratory rate)
- Pulse oximetry
- Weight
- Spirometry
- Clinical laboratory tests (serum chemistry, hematology, coagulation, urinalysis, C-reactive protein [CRP])
- ECG
- AE/serious adverse event (SAE) reporting
- Recording of concomitant medications and concomitant surgical procedures
- Serum or urine pregnancy test
- Testing for immune response assays, inflammatory markers, and/or [REDACTED] mRNA and [REDACTED] assays at the discretion of the Investigator and/or Sponsor

